#### **8.4.8 Other Analyses**

Not applicable.

#### **8.5 Interim Analyses**

Within each tumor type, an interim analysis (IA) will be conducted when all subjects in the Dose Evaluation Phase have a minimum of 3 months of treatment or discontinued prematurely. The objectives of this IA will be: 1) to determine if further study of ulocuplumab combined with nivolumab is warranted in the tumor type; 2) if further study is warranted, to select a recommended dose for the Dose Expansion Phase; and 3) if the Dose Expansion Phase is to be completed, to determine whether to conduct a single arm second stage of a Simon optimal 2 stage like design or an open label randomized Phase 2 design with a comparative arm.

The decision to further study ulocuplumab combined with nivolumab in each tumor type will primarily be based on the pre-defined Simon 2-stage design thresholds for the Dose Evaluation Phase (at least 4 responders for SCLC and at least 2 responders for PAC). In addition, the selection of the recommended dose will be based on all available safety and efficacy data for that IA from both tumor types. The decision to proceed from the Dose Evaluation Phase to the Dose Expansion Phase will be conducted for each tumor type independently. Consideration may be given to evaluating final data before decision is reached to stop further study the combination to ensure the full characterization of the response pattern is evaluated.

The decision to proceed with an open label randomized two-arm Phase 2 design rather than completing the second stage of a Simon optimal 2-stage like design for the Expansion Phase will be taken if, among the treated subjects in the recommended dose selected during the Dose Evaluation Phase, a “high” frequency of responders is observed. For SCLC, this “high” number will be at least 9 responders and, for PAC, at least 6 responders.

This number of responders has been defined considering clinical input but, ensuring that the related proportion of responders also presents with a 90% exact CI lower limit above 25% for SCLC or above 12% for PAC. These percentages correspond to the minimum proportion of responders that would be needed at the end of a Simon 2-stage design in order to further evaluate

the drug (for SCLC, 11 responders among the 44 subjects is 25% and, for PAC, 5 responders among the 41 subjects is 12%).

During the Expansion phase, an IA will be conducted when all subjects of the second stage of the Simon 2-stage like design have a minimum of 3 months of treatment or discontinued prematurely. If a randomized Phase 2 study with comparative arm is initiated, IA will be conducted for the DMC as specified in the DMC charter on a regular basis.

## **9 STUDY MANAGEMENT**

### **9.1 Compliance**

#### **9.1.1 Compliance with the Protocol and Protocol Revisions**

The study shall be conducted as described in this approved protocol. All revisions to the protocol must be discussed with, and be prepared by, BMS. The investigator should not implement any deviation or change to the protocol without prior review and documented approval/favorable opinion from the IRB/IEC of an amendment, except where necessary to eliminate an immediate hazard(s) to study subjects.

If a deviation or change to a protocol is implemented to eliminate an immediate hazard(s) prior to obtaining IRB/IEC approval/favorable opinion, as soon as possible the deviation or change will be submitted to:

- IRB/IEC for review and approval/favorable opinion
- BMS
- Regulatory Authority(ies), if required by local regulations

Documentation of approval signed by the chairperson or designee of the IRB(s)/IEC(s) must be sent to BMS.

If an amendment substantially alters the study design or increases the potential risk to the subject: (1) the consent form must be revised and submitted to the IRB(s)/IEC(s) for review and approval/favorable opinion; (2) the revised form must be used to obtain consent from subjects currently enrolled in the study if they are affected by the amendment; and (3) the new form must be used to obtain consent from new subjects prior to enrollment.

If the revision is done via an administrative letter, investigators must inform their IRB(s)/IEC(s).

#### **9.1.2 Monitoring**

BMS representatives will review data centrally to identify potential issues to determine a schedule of on-site visits for targeted review of study records.

Representatives of BMS must be allowed to visit all study site locations periodically to assess the data quality and study integrity. On site they will review study records and directly compare them with source documents, discuss the conduct of the study with the investigator, and verify that the facilities remain acceptable.

In addition, the study may be evaluated by BMS internal auditors and government inspectors who must be allowed access to CRFs, source documents, other study files, and study facilities. BMS audit reports will be kept confidential.

The investigator must notify BMS promptly of any inspections scheduled by regulatory authorities, and promptly forward copies of inspection reports to BMS.

#### **9.1.2.1 Source Documentation**

The investigator is responsible for ensuring that the source data are accurate, legible, contemporaneous, original and attributable, whether the data are hand-written on paper or entered electronically. If source data are created (first entered), modified, maintained, archived, retrieved, or transmitted electronically via computerized systems (and/or any other kind of electronic devices) as part of regulated clinical trial activities, such systems must be compliant with all applicable laws and regulations governing use of electronic records and/or electronic signatures. Such systems may include, but are not limited to, electronic medical/health records (EMRs/EHRs), adverse event tracking/reporting, protocol required assessments, and/or drug accountability records).

When paper records from such systems are used in place of electronic format to perform regulated activities, such paper records should be certified copies. A certified copy consists of a copy of original information that has been verified, as indicated by a dated signature, as an exact copy having all of the same attributes and information as the original.

#### **9.1.3 Investigational Site Training**

Bristol-Myers Squibb will provide quality investigational staff training prior to study initiation. Training topics will include but are not limited to: GCP, AE reporting, study details and procedure, electronic CRFs, study documentation, informed consent, and enrollment of WOCBP.

### **9.2 Records**

#### **9.2.1 Records Retention**

The investigator must retain all study records and source documents for the maximum period required by applicable regulations and guidelines, or institution procedures, or for the period specified by BMS, whichever is longer. The investigator must contact BMS prior to destroying any records associated with the study.

BMS will notify the investigator when the study records are no longer needed.

If the investigator withdraws from the study (eg, relocation, retirement), the records shall be transferred to a mutually agreed upon designee (eg, another investigator, IRB). Notice of such transfer will be given in writing to BMS.

#### **9.2.2 Study Drug Records**

It is the responsibility of the investigator to ensure that a current disposition record of study drug (inventoried and dispensed) is maintained at the study site to include investigational product and the following non-investigational product(s): For PAC subjects, if Stage 1 results in a decision to move to a randomized Phase 2 study with comparative arm in Dose Expansion Phase,

Investigator's Choice for advanced or metastatic PAC subjects will be the comparator arm. The treatment options for 2L PAC include the following:

- Gemcitabine with or without albumin-bound paclitaxel
- Capecitabine and other fluoropyrimidine containing regimens

Records or logs must comply with applicable regulations and guidelines and should include:

- amount received and placed in storage area
- amount currently in storage area
- label identification number or batch number
- amount dispensed to and returned by each subject, including unique subject identifiers
- amount transferred to another area/site for dispensing or storage
- nonstudy disposition (eg, lost, wasted)
- amount destroyed at study site, if applicable
- amount returned to BMS
- retain samples for bioavailability/bioequivalence, if applicable
- dates and initials of person responsible for Investigational Product dispensing/accountability, as per the Delegation of Authority Form

BMS will provide forms to facilitate inventory control if the investigational site does not have an established system that meets these requirements.

### **9.2.3 Case Report Forms**

An investigator is required to prepare and maintain adequate and accurate case histories designed to record all observations and other data pertinent to the investigation on each individual treated or entered as a control in the investigation. Data that are derived from source documents and reported on the CRF must be consistent with the source documents or the discrepancies must be explained. Additional clinical information may be collected and analyzed in an effort to enhance understanding of product safety. CRFs may be requested for AEs and/or laboratory abnormalities that are reported or identified during the course of the study.

For sites using the BMS electronic data capture tool, electronic CRFs will be prepared for all data collection fields except for fields specific to SAEs and pregnancy, which will be reported on the paper or electronic SAE form and Pregnancy Surveillance form, respectively. Spaces may be left blank only in those circumstances permitted by study-specific CRF completion guidelines provided by BMS.

The confidentiality of records that could identify subjects must be protected, respecting the privacy and confidentiality rules in accordance with the applicable regulatory requirement(s).

The investigator will maintain a signature sheet to document signatures and initials of all persons authorized to make entries and/or corrections on CRFs.

The completed CRF, including any paper or electronic SAE/pregnancy CRFs, must be promptly reviewed, signed, and dated by the investigator or qualified physician who is a sub-investigator and who is delegated this task on the Delegation of Authority Form. For electronic CRFs, review and approval/signature is completed electronically through the BMS electronic data capture tool. The investigator must retain a copy of the CRFs including records of the changes and corrections.

Each individual electronically signing electronic CRFs must meet BMS training requirements and must only access the BMS electronic data capture tool using the unique user account provided by BMS. User accounts are not to be shared or reassigned to other individuals.

### **9.3 Clinical Study Report and Publications**

A Signatory Investigator must be selected to sign the clinical study report.

For this protocol, the Signatory Investigator will be selected as appropriate based on the following criteria:

- External Principal Investigator designated at protocol development
- Subject recruitment (eg, among the top quartile of enrollers)
- Regional representation (eg, among top quartile of enrollers from a specified region or country)
- Other criteria (as determined by the study team)

The data collected during this study are confidential and proprietary to BMS. Any publications or abstracts arising from this study must adhere to the publication requirements set forth in the clinical trial agreement (CTA) governing [Study site or Investigator] participation in the study. These requirements include, but are not limited to, submitting proposed publications to BMS at the earliest practicable time prior to submission or presentation and otherwise within the time period set forth in the CTA.

## 10 GLOSSARY OF TERMS

Term	Definition
Complete Abstinence	
If one form of contraception is required, Complete Abstinence is defined as complete avoidance of heterosexual intercourse and is an acceptable form of contraception for all study drugs. Female subjects must continue to have pregnancy tests. Acceptable alternate methods of highly effective contraception must be discussed in the event that the subject chooses to forego complete abstinence.
 
If two forms of contraception is required, Complete abstinence is defined as complete avoidance of heterosexual intercourse and is an acceptable form of contraception for all study drugs. Subjects who choose complete abstinence are not required to use a second method of contraception, but female subjects must continue to have pregnancy tests. Acceptable alternate methods of highly effective contraception must be discussed in the event that the subject chooses to forego complete abstinence.
 
Expanded definition Complete abstinence as defined as complete avoidance of heterosexual intercourse is an acceptable form of contraception for all study drugs. This also means that abstinence is the preferred and usual lifestyle of the patient. This does not mean periodic abstinence (eg, calendar, ovulation, symptothermal, profession of abstinence for entry into a clinical trial, post-ovulation methods) and withdrawal, which are not acceptable methods of contraception. Subjects who choose complete abstinence are not required to use a second method of contraception, but female subjects must continue to have pregnancy tests. Acceptable alternate methods of highly effective contraception must be discussed in the event that the subject chooses to forego complete abstinence

## 11 LIST OF ABBREVIATIONS

Term	Definition
ACTH	Adrenocorticotrophic hormone
AE	Adverse Event
AIDS	Acquired Immune Deficiency Syndrome
ALP	Alkaline Phosphatase
ALT	alanine aminotransferase
AML	Acute Myeloid Leukemia
ANC	absolute neutrophil count
ANOVA	analysis of variance
AST	aspartate aminotransferase
AT	aminotransaminases
AUC	Area Under the Curve
BMS	Bristol-Myers Squibb
BOR	Best Overall Response
BP	blood pressure
BUN	Blood Urea Nitrogen
Ca ++	Calcium
CAF	Cancer Associated Fibroblast
CA19.9	Cancer Antigen 19.9
CBC	complete blood count
CI	confidence interval
CLL	Chronic Lymphocytic Leukemia
C max , C MAX	maximum observed concentration
C min , C MIN	trough observed concentration
CR	Complete response
CrCl	Creatinine Clearance
CRF	Case Report Form, paper or electronic
CRP	C Reactive Protein
CT	Computed tomography
CTA	Clinical Trial Agreement

Term	Definition
CTCAE	Common Terminology Criteria for Adverse Events
CTLA-4	Cytotoxic T-lymphocyte-associated protein 4
CV	coefficient of variation
CXCR4	CXC Chemokine Receptor 4
DCR	Disease control rate
DILI	Drug Induced Liver Injury
DL	Dose Level
DLBCL	Diffuse Large B Cell Leukemia
DLT	Dose limiting toxicity
DMC	Data Monitoring Committee
DOR	Duration of response
ECG	Electrocardiogram
ECOG	Eastern Cooperative Oncology Group
ED-SCLC	Extensive Disease Small Cell Lung Cancer
EQ-VAS	EQ visual analog scale
EMR	Electronic Medical Records
EHR	Electronic Health Records
EOI	End of Infusion
EQ-5D	EuroQol 5 Dimensions Questionnaire
FAP	Fibroblast Activating Protein
FDA	Food and Drug Administration
FDG/PET	18-Fluoro-deoxyglucose positron emission tomography
FFPE	Formalin-fixed, paraffin-embedded
FL	Follicular Lymphoma
FOLFIRINOX	combination of 5-FU, leucovorin, irinotecan, oxaliplatin
FSH	follicle stimulating hormone
FU1	Follow-up 1
FU2	Follow-up 2
GCP	Good Clinical Practice
GEM	Gemcitabine

Term	Definition
HBsAg	hepatitis B surface antigen
HBV	hepatitis B virus
HCC	hepatocellular carcinoma
HCG	human chorionic gonadotropin
HCV	hepatitis C virus
HIV	Human Immunodeficiency Virus
HR	heart rate
HRT	Hormonal Replacement Therapy
IRB	Institutional Review Board
IA	Interim Analysis
IB	Investigator Brochure
IC	Informed Consent
ICH	International Conference on Harmonisation
IEC	Independent Ethics Committee
IRRC	Independent Radiology Review Committee
IV	Intravenous
IVRS	interactive voice response system
KM	Kaplan-Meier
LD-SCLC	Limited Disease - Small Cell Lung Cancer
LDH	Lactate Dehydrogenase
LFT	Liver Function Tests
MEC	mitoxantrone, etoposide, and cytarabine
MM	Multiple Myeloma
MST	medical safety team
MRI	Magnetic resonance imaging
MTD	maximum tolerated dose
N	Nivolumab
N/A	not applicable
NCCN	National Comprehensive Cancer Network
NCI	National Cancer Institute

Term	Definition
NIMP	non-investigational medicinal products
NK	Natural Killer
NSAID	nonsteroidal anti-inflammatory drug
NSCLC	Non-small cell lung cancer
ORR	Objective response rate
OS	Overall survival
PBMC	Peripheral blood mononuclear cell
PAC	Pancreatic adenocarcinoma
PD	Pharmacodynamics
PDAC	Pancreatic ductal adenocarcinoma
PD-1	Programmed death 1
PD-L1	Programmed cell death 1 ligand 1
PE	Physical Exam
PE	Platinum plus etoposide
PFS	Progression-Free Survival
PK	Pharmacokinetics
PR	Partial response
Q2W	Every two weeks
QC	quality control
RCC	Renal Cell Carcinoma
RNA	Ribonucleic Acid
RBC	red blood cell
RO	Receptor Occupancy
RECIST	Response Evaluation Criteria in Solid Tumors
RT-PCR	Reverse transcription-polymerase chain reaction
SAE	serious adverse event
SCLC	Small cell lung cancer
SD	stable disease
SDF-1	stromal cell-derived factor 1
SOC	Standard of care

Term	Definition
T3, T4	triiodothyronine (T3), thyroxine (T4)
TSH	Thyroid Stimulating Hormone
U	Ulocuplumab
ULN	Upper Limit of Normal
US	United States
VGPR	Very Good Partial Response
WBC	white blood cell
WHO	World Health Organization
WOCBP	women of childbearing potential
2L	Second Line

**APPENDIX 1 PERFORMANCE STATUS SCALES**

STATUS	SCALES		STATUS
	KARNOFSKY	ZUBROD- ECOG-WHO	
Normal, no complaints	100	0	Normal activity
Able to carry on normal activities Minor signs or symptoms of disease	90	0	Symptoms, but fully ambulatory
Normal activity with effort	80	1	
Cares for self. Unable to carry on normal activity or to do active work	70	1	Symptomatic, but in bed < 50% of the day.
Requires occasional assistance, but able to care for most of his needs	60	2	
Requires considerable assistance and frequent medical care	50	2	Needs to be in bed > 50% of the day, but not bedridden
Disabled. Requires special care and assistance	40	3	
Severely disabled. Hospitalization indicated though death non imminent	30	3	
Very sick. Hospitalization necessary. Active supportive treatment necessary	20	4	Unable to get out of bed
Moribund	10	4	
Dead	0	5	Dead

## **APPENDIX 2           MANAGEMENT ALGORITHMS**

These general guidelines constitute guidance to the Investigator and may be supplemented by discussions with the Medical Monitor representing the Sponsor. The guidance applies to all immuno-oncology (I-O) agents and regimens.

A general principle is that differential diagnoses should be diligently evaluated according to standard medical practice. Non-inflammatory etiologies should be considered and appropriately treated.

[figure not shown]
Corticosteroids are a primary therapy for immuno-oncology drug-related adverse events. The oral equivalent of the recommended IV doses may be considered for ambulatory patients with low-grade toxicity. The lower bioavailability of oral corticosteroids should be taken into account when switching to the equivalent dose of oral corticosteroids.

Consultation with a medical or surgical specialist, especially prior to an invasive diagnostic or therapeutic procedure, is recommended.

The frequency and severity of the related adverse events covered by these algorithms will depend on the immuno-oncology agent or regimen being used.

## GI Adverse Event Management Algorithm

[figure not shown]
Rule out non-inflammatory causes. If non-inflammatory cause is identified, treat accordingly and continue I-O therapy. Opiates/narcotics may mask symptoms of perforation. Infliximab should not be used in cases of perforation or sepsis.

Patients on IV steroids may be switched to an equivalent dose of oral corticosteroids (e.g. prednisone) at start of tapering or earlier, once sustained clinical improvement is observed. Lower bioavailability of oral corticosteroids should be taken into account when switching to the equivalent dose of oral corticosteroids.

## Renal Adverse Event Management Algorithm

[figure not shown]
Rule out non-inflammatory causes. If non-inflammatory cause, treat accordingly and continue I-O therapy

Patients on IV steroids may be switched to an equivalent dose of oral corticosteroids (e.g. prednisone) at start of tapering or earlier, once sustained clinical improvement is observed. Lower bioavailability of oral corticosteroids should be taken into account when switching to the equivalent dose of oral corticosteroids.

## Pulmonary Adverse Event Management Algorithm

[figure not shown]
Rule out non-inflammatory causes. If non-inflammatory cause, treat accordingly and continue I-O therapy. Evaluate with imaging and pulmonary consultation.

Patients on IV steroids may be switched to an equivalent dose of oral corticosteroids (e.g. prednisone) at start of tapering or earlier, once sustained clinical improvement is observed. Lower bioavailability of oral corticosteroids should be taken into account when switching to the equivalent dose of oral corticosteroids.

## Hepatic Adverse Event Management Algorithm

Rule out non-inflammatory causes. If non-inflammatory cause, treat accordingly and continue I-O therapy. Consider imaging for obstruction.

[figure not shown]
Patients on IV steroids may be switched to an equivalent dose of oral corticosteroids (e.g. prednisone) at start of tapering or earlier, once sustained clinical improvement is observed. Lower bioavailability of oral corticosteroids should be taken into account when switching to the equivalent dose of oral corticosteroids.

\*I-O therapy may be delayed rather than discontinued if AST/ALT ≤ 8 x ULN and T.bili ≤ 5 x ULN.

\*\*The recommended starting dose for grade 4 hepatitis is 2 mg/kg/day methylprednisolone IV.

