### **3.5 Discontinuation of Subjects following any Treatment with Study Drug**

Subjects MUST discontinue investigational product (and non-investigational product at the discretion of the investigator) for any of the following reasons:

- Subject's request to stop study treatment
- Any clinical AE, laboratory abnormality or intercurrent illness which, in the opinion of the investigator, indicates that continued participation in the study is not in the best interest of the subject
- Termination of the study by Bristol-Myers Squibb (BMS)
- Loss of ability to freely provide consent through imprisonment or involuntarily incarceration for treatment of either a psychiatric or physical (eg, infectious disease) illness
- Pregnancy
- Additional protocol specific reasons for discontinuation (see [Sections 4.5.3.1](#) and [4.5.3.2](#))

All subjects who discontinue study drug should comply with protocol specified follow-up procedures as outlined in [Section 5](#). The only exception to this requirement is when a subject withdraws consent for all study procedures including post-treatment study follow-up or loses the ability to consent freely (ie, is imprisoned or involuntarily incarcerated for the treatment of either a psychiatric or physical illness).

If study drug is discontinued prior to the subject's completion of the study, the reason for the discontinuation must be documented in the subject's medical records and entered on the appropriate case report form (CRF) page.

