#### **4.5.1.2 Nivolumab Dose Delay**

Investigators should, whenever possible, determine which medication is causing the toxicity and delay or dose reduce ulocuplumab and/or delay nivolumab, as applicable. If nivolumab is delayed due to an AE, ulocuplumab dosing should also be delayed. Nivolumab should be delayed for the following:

- Any Grade  $\geq 2$  non-skin, drug-related AE, with the following exceptions:
  - Grade 2 drug-related fatigue or laboratory abnormalities do not require a treatment delay
- Any Grade 3 skin drug-related AE
- Any Grade  $\geq 3$  drug-related laboratory abnormality, with the following exceptions for thrombocytopenia, lymphocytopenia, AST, ALT, total bilirubin or asymptomatic amylase or lipase:
  - Grade 3 thrombocytopenia  $< 7$  days (not associated with Grade  $\geq 2$  hemorrhage) does not require dose delay
  - Grade 3 lymphocytopenia not associated with symptoms or clinical manifestations does not require dose delay. It is recommended to consult with the BMS Medical Monitor for Grade 3 lymphocytopenia.
  - Grade 3 drug-related amylase or lipase abnormality that is not associated with symptoms or clinical manifestations of pancreatitis does not require dose delay. It is recommended to consult with the BMS Medical Monitor for Grade 3 amylase or lipase abnormalities
  - If a subject has baseline AST, ALT, or total bilirubin that is within normal limits, delay dosing for drug-related Grade  $\geq 2$  toxicity
  - If a subject has baseline AST, ALT, or total bilirubin within the Grade 1 toxicity range, delay dosing for drug-related Grade  $\geq 3$  toxicity
  - If a subject has baseline AST or ALT within the Grade 2 toxicity range, delay dosing for drug-related elevations in AST and/or ALT  $> 2x$  baseline or a maximum of  $> 8x$  ULN
- Any adverse event, laboratory abnormality, or intercurrent illness which, in the judgment of the investigator, warrants delaying the dose of study medication

If the decision is to resume nivolumab dosing, the subject should restart treatment on the next regularly scheduled nivolumab dosing visit. Skipped doses are not to be replaced. If treatment is delayed  $> 6$  weeks, the subject must be permanently discontinued from all study therapy, except as specified in [Section 4.5.3.2](#).

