Because of the potential for nivolumab-related AE requiring early recognition and prompt intervention, management algorithms have been developed and are included for suspected pulmonary toxicity, GI toxicity, hepatotoxicity, endocrinopathy, skin toxicity, neurological toxicity and nephrotoxicity. In order to standardize the management of AEs for all subjects, recommended treatment management algorithms are included in [Appendix 2](#). Adverse event treatment management algorithms included in the nivolumab IB might be considered for individual cases.

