### **4.5.1.3 Criteria to Resume Nivolumab Treatment**

Subjects may resume treatment with nivolumab when the drug-related AE resolves to Grade  $\leq$  1 or baseline value, with the following exceptions:

- Subjects may resume treatment in the presence of Grade 2 fatigue
- Subjects who have not experienced a Grade 3 drug-related skin AE may resume treatment in the presence of a Grade 2 toxicity
- Subjects with baseline AST/ALT or total bilirubin in the Grade 1 or 2 toxicity range who require dose delays for reasons other than a 1 or 2-grade shift in AST/ALT or total bilirubin may resume treatment in the presence of Grade 2 AST/ALT OR total bilirubin
  - Subjects with combined Grade 2 AST/ALT AND total bilirubin values meeting discontinuation parameters ([Section 4.5.3.2](#)) should have treatment permanently discontinued
- Drug-related pulmonary toxicity, diarrhea, or colitis must have resolved to baseline before treatment is resumed
- Drug-related endocrinopathies adequately controlled with only physiologic hormone replacement may resume treatment

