#### **4.5.3.2 Nivolumab Discontinuation Criteria**

Discontinuation criteria apply for all drug-related AE attributed to nivolumab and consist of the following:

- Any Grade 2 drug-related uveitis, eye pain, or blurred vision that does not respond to topical therapy and does not improve to Grade 1 severity within the re-treatment period OR requires systemic treatment
- Any Grade 3 non-skin, drug-related adverse event lasting  $> 7$  days, with the following exceptions for drug-related laboratory abnormalities, uveitis, pneumonitis, bronchospasm, diarrhea, colitis, neurological toxicity, hypersensitivity reactions, and infusion reactions:
  - Grade 3 drug-related uveitis, pneumonitis, bronchospasm, diarrhea, colitis, neurologic toxicity, hypersensitivity reaction, or infusion reaction of any duration requires discontinuation
  - Grade 3 drug-related endocrinopathies adequately controlled with only physiologic hormone replacement do not require discontinuation
  - Grade 3 drug-related laboratory abnormalities do not require treatment discontinuation except:
    - ◆ Grade 3 drug-related thrombocytopenia associated with bleeding requires discontinuation
    - ◆ Any drug-related liver function test (LFT) abnormality that meets the following criteria require discontinuation:
      - If a subject has a baseline AST or ALT within normal limits:
        - AST or ALT  $> 5-8x$  ULN for  $> 2$  weeks
        - AST or ALT  $> 8x$  ULN, irrespective of duration
        - Concurrent AST or ALT  $> 3x$  ULN and total bilirubin  $> 2x$  ULN
      - If a subject has a baseline AST or ALT within Grade 1 or 2 toxicity range:
        - AST or ALT  $> 10x$  ULN for  $> 2$  weeks
        - AST or ALT  $> 15x$  ULN, irrespective of duration
        - Total bilirubin  $> 5x$  ULN
        - Concurrent AST or ALT  $> 3x$  ULN and total bilirubin  $> 2x$  ULN

- Any Grade 4 non-skin drug-related adverse event or laboratory abnormality, except for the following events which do not require discontinuation:
  - Isolated Grade 4 electrolyte imbalances/abnormalities that are not associated with clinical sequelae and are corrected with supplementation/appropriate management within 72 hours of their onset
  - Grade 4 thrombocytopenia or neutropenia < 5 days
  - Grade 4 lymphocytopenia or leukopenia not associated with symptoms or clinical manifestations. It is recommended to consult with the BMS Medical Monitor for Grade 4 lymphocytopenia.

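### The hepatic footnote in Appendix 2 permits a treatment delay at liver values for which section 4.5.3.2 requires discontinuation

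*Protocol*

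**What the plan says.** The Protocol addresses the choice between delaying and stopping treatment for liver toxicity in two places.

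- **Appendix 2, Hepatic Adverse Event Management Algorithm.** The asterisked footnote states: "I-O therapy may be delayed rather than discontinued if AST/ALT" is no higher than 8 x ULN and total bilirubin no higher than 5 x ULN. Nothing else limits it.
- **Section 4.5.3.2, Nivolumab Discontinuation Criteria.** The text reads: "Any drug-related liver function test (LFT) abnormality that meets the following criteria require discontinuation". Three criteria follow for a normal AST/ALT baseline and four for a baseline in the Grade 1 or 2 range.

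Section 3.5 makes these criteria mandatory. Its list of reasons for which subjects must stop includes "Additional protocol specific reasons for discontinuation", with a reference to sections 4.5.3.1 and 4.5.3.2. Appendix 2 describes itself as guidance. Section 4.5.1.2 introduces the algorithms this way: "In order to standardize the management of AEs for all subjects, recommended treatment management algorithms are included in" Appendix 2.

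**The concern.** For part of the liver-value range, the footnote grants a permission that the body of the Protocol withholds. The main overlap is combined transaminase and bilirubin elevation, and section 6.6 uses the same cut-offs of 3 x and 2 x ULN in its definition of potential drug-induced liver injury.

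A site working from the algorithm page could delay treatment in such a subject and later restart it. Section 4.5.1.3 opens the way: "Subjects may resume treatment with nivolumab when the drug-related AE resolves to Grade" 1 or below, or to the baseline value. That section does carry a reminder, "Subjects with combined Grade 2 AST/ALT AND total bilirubin values meeting discontinuation parameters", directing permanent discontinuation. However, it is nested under the bullet for subjects whose baseline was already Grade 1 or 2, so it does not reach a subject with a normal baseline.

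DLT counting is a secondary matter. Section 3.1.4 counts any toxicity managed by stopping nivolumab as a DLT, so the choice between delay and discontinuation could in principle alter the count. The effect is limited, because a drug-related Grade 3 or higher liver value with baseline Grade 1 or below is a DLT in any case.

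**Working it through.** There is no sample size, power or alpha figure to reproduce. The check sets the two rules side by side.

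**Inputs**

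- Footnote range (Appendix 2): AST/ALT ≤ 8 x ULN and bilirubin ≤ 5 x ULN.
- Discontinuation criteria: the seven liver criteria in section 4.5.3.2.
- Initial delay rule (section 4.5.1.2).

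**Step 1. Each criterion against the footnote range**

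| No. | Baseline AST/ALT | Discontinue when (x ULN) | Against the footnote range |
|---|---|---|---|
| 1 | Normal | AST/ALT above 5 and up to 8, longer than 2 weeks | Overlaps |
| 2 | Normal | AST/ALT above 8, any duration | Outside |
| 3 | Normal | AST/ALT above 3 with bilirubin above 2 | Overlaps |
| 4 | Grade 1-2 | AST/ALT above 10, longer than 2 weeks | Outside |
| 5 | Grade 1-2 | AST/ALT above 15, any duration | Outside |
| 6 | Grade 1-2 | Bilirubin above 5 | Outside |
| 7 | Grade 1-2 | AST/ALT above 3 with bilirubin above 2 | Overlaps |

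Three of seven overlap. Numbers 3 and 7 are the same rule, so there are two distinct rules in conflict. The footnote's limits coincide with the single-value cut-offs in numbers 2 and 6 and leave out the concurrent and duration criteria.

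**Step 2. Regions of conflict**

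- *Concurrent rule, any baseline and any duration:* AST/ALT above 3 and up to 8 x ULN, with bilirubin above 2 and up to 5 x ULN.
- *Duration rule, normal baseline only:* AST/ALT above 5 and up to 8 x ULN for more than 2 weeks, even with bilirubin at or below 2 x ULN.

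The second conflict starts only after 2 weeks. Before that, delay is the correct first step under section 4.5.1.2: "If a subject has baseline AST, ALT, or total bilirubin that is within normal limits, delay dosing for drug-related Grade" 2 or above.

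**Step 3. Examples**

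- AST 6 x, bilirubin 2.5 x ULN. Footnote: 6 ≤ 8 and 2.5 ≤ 5, so delay is allowed. Section 4.5.3.2: 6 > 3 and 2.5 > 2, so discontinuation is required.
- AST 7 x, bilirubin 1 x ULN, normal baseline, week 3. Footnote: 7 ≤ 8 and 1 ≤ 5, so delay is allowed. Section 4.5.3.2: above 5 x for more than 2 weeks, so discontinuation is required. At week 1 the same values do not conflict.

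**Step 4. Grid check**

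Both rules were coded and compared on a grid in steps of 0.5 (AST/ALT 1 to 16 x ULN, bilirubin 0.5 to 6 x ULN). The footnote range holds 15 × 10 = 150 grid points.

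- Up to 2 weeks, either baseline: 60 points conflict (10 AST/ALT values from 3.5 to 8, times 6 bilirubin values from 2.5 to 5).
- Beyond 2 weeks, Grade 1-2 baseline: still 60.
- Beyond 2 weeks, normal baseline: 84, the extra 24 being 6 AST/ALT values from 5.5 to 8 times 4 bilirubin values from 0.5 to 2.

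These counts describe the extent of the overlap in the rules. They say nothing about how often subjects have such values.

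**The case against.** The strongest reply is that the binding text is clear. Section 3.5 says subjects must stop for the section 4.5.3.2 reasons, and that section lists its own exceptions without mentioning Appendix 2. The footnote only says that delay is possible, in an appendix that calls itself guidance for all immuno-oncology agents. A site that discontinues complies with both texts. This stands as the better reading and lowers the weight of the point. It does not remove the point: precedence is left to inference, and section 4.5.1.2 presents the algorithms as the means of standardising management.

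A second reply is that the algorithm figure is missing from the text available, so the box carrying the asterisk is unknown. That uncertainty is real. However, the footnote's limits are complete in themselves, and it is worded as an exception to discontinuation. Even a box restricted to Grade 3-4 would leave the example of 6 x with 2.5 x ULN in conflict, assuming that AST Grade 3 starts above 5 x ULN.

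A third reply is that three of seven overstates the matter. It is fair that two of the three are one rule printed twice. It is also fair that the footnote's silence on duration can be read as delay first and discontinuation after 2 weeks. The concurrent rule at normal baseline is the clearest conflict.

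Finally, harm would need several failures in a row. A case meeting the full definition in section 6.6 is an SAE, reportable within 24 hours (section 6.1.1), and the Medical Monitor reviews safety continuously (section 7). After a delay of more than 6 weeks, "the subject must be permanently discontinued from all study therapy", apart from exceptions such as prolonged steroid tapers, which need Medical Monitor consultation. These safeguards limit the risk. They do not correct the instruction.

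**Conclusion.** The concern holds. As written, the footnote allows delay in a range where section 4.5.3.2 requires discontinuation, and following it would give the wrong safety action. The conflict covers three of the seven listed liver criteria, or two distinct rules. The other four lie outside the footnote's range.

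The point is of low-to-moderate weight for patient safety and should be corrected. Confidence is medium, for two reasons: the figure is not available, and the likely precedence of section 4.5.3.2 is inferred. The size in subjects cannot be estimated from the documents. The conclusion applies to drug-related abnormalities, as section 4.5.3.2 does.

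**What to change.** Amend the footnote so that the permission to delay is subject to section 4.5.3.2. Say that delay is not permitted in two situations: AST or ALT above 3 x ULN concurrent with total bilirubin above 2 x ULN; and, with a normal baseline, AST or ALT above 5 and up to 8 x ULN once it has lasted more than 2 weeks. Add one sentence to the opening of Appendix 2 stating that section 4.5.3.2 governs wherever the two differ.

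If the sponsor prefers not to repeat thresholds that would later have to be kept in step, the cross-reference and the precedence sentence would resolve the conflict on their own. Naming the two exclusions helps staff who read only the algorithm page.

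The cost is a wording change in the next protocol amendment, with the IRB/IEC approval described in section 9.1.1. Sample size, analyses and decision thresholds are unaffected.
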